**41. \* Provide justification for the sample size:**

42 Sample size: Prior studies and our cohort have shown a 30-day readmission rate around 33% using current practice, and of which 20% were  
43 considered avoidable. Per our preliminary data, the rate of 30-day avoidable readmission reduced to 5%. However, we will be circumspect  
44 and increase this relative avoidable readmission rate to 9%. In order to determine a similar reduction at 80% power at an  $\alpha = 0.05$  level of  
45 significance we would require 45 patients in the Health-IT+scheduled visits, 45 patients in the Health- IT only and 45 patients in the standard  
46 of care group per site leading to a total of 135 patients per site or 405 total patients. This will also include 405 caregivers. Allowing for a 10%  
47 dropout rate, we plan to we will enroll a total of 450 patients, of which 150 will be randomized to health-IT+scheduled visits, 150 to health-IT  
48 only and 150 to standard of care across all three sites. This will be accompanied by an equal number of the respective caregivers bringing the  
49 grand total of subjects across all three sites to 900.

50 Therefore at McGuire VAMC we will enroll 50 patients and 50 caregivers in each group for a total of 300 subjects (150 patients and  
50 caregivers).

51

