12 Justification: To increase generalizability  
13

14 **Protocol Amendment 2**  
15

16 Due to COVID-19 related gap in enrollment, funding shortfalls, and low likelihood of us reaching the  
17 original study goals, a re-evaluation of the data was done to see if we could combine the two health-IT  
18 groups. Avoidable readmissions were similar across the 2 health IT groups and therefore, instead of 1:1:1  
19 randomization, this was changed to 1:1 randomization with a total of 464 subjects ( 232 patients and 232  
20 caregivers).  
21

22 Justification: reduced enrolment requiring combination of the groups.  
23

24  
25  
26  
27  
28  
29  
30  
31  
32  
33  
34  
35  
36  
37  
38  
39  
40  
41  
42  
43  
44  
45  
46  
47  
48  
49  
50  
51  
52  
53  
54  
55  
56  
57  
58  
59

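### Amendment 2 resizes the trial to 232 patients at 1:1 without restating power; on the planning rates that reproduce the original size, power is about 66%

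*Combined protocol and SAP*

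**What the plan says.** The sample-size justification (Study Population) starts from a "30-day readmission rate around 33% using current practice, and of which 20% were" judged avoidable. It cites a rate of 5% from preliminary data, then chooses to be cautious: "and increase this relative avoidable readmission rate to 9" percent. The size follows: "In order to determine a similar reduction at 80% power" at alpha 0.05, the plan needs 45 patients in each of three groups at each of three sites, or 405 in all. A 10% dropout allowance raises this to 450 enrolled, 150 per group. Neither the test nor its sidedness is stated.

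Protocol Amendment 2, in the list of changes at the end of the document, cites the COVID-19 enrolment gap, funding and the low chance of reaching the original goals. It combines the two health-IT groups and replaces 1:1:1 allocation: "this was changed to 1:1 randomization with a total of 464 subjects", made up of 232 patients and 232 caregivers. It says nothing about power, the difference the new size can detect, the rates assumed or dropout. It does not say how patients already randomised 1:1:1 count towards the 232.

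**The concern.** The number of patients falls from 450 to 232 and the comparison changes from three groups to two, yet the only power figure in the document belongs to the design that was replaced. A reader who wants the power of the trial now being run finds only 80%. If the true figure is nearer two in three, a real effect of the planned size would be missed about one time in three. A non-significant result could then be given more weight as evidence against the intervention than the trial can bear.

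**Working it through.** **Inputs.** From the sample-size section: alpha 0.05, 80% power, rates 33%, 20%, 5% and 9%, 135 per group (45 × 3 sites), 405 evaluable, 10% dropout. From Amendment 2: 232 patients, 1:1. Assumed here: a two-sided test, 116 per arm (232 / 2), and 20% and 9% as proportions of all patients in an arm.

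**Step 1: reproduce the plan's figure.** For a three-group chi-square test (2 df) on 20%, 9% and 9%:
- mean rate = (0.20 + 0.09 + 0.09) / 3 = 0.1267
- sum of squared deviations = 0.00807
- noncentrality at 135 per group = 135 × 0.00807 / (0.1267 × 0.8733) = 9.84
- power against the critical value 5.99 = 80.9% (78.8% by simulation)
- size for 80% = 133 per group, 399 in total, close to 405
- dropout: 405 / 0.9 = 450, as stated

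So 20/9/9 as patient-level rates accounts for the plan's size. A two-group formula on 20% vs 9% does not: it needs 160 per group, and 135 per group gives 73.1%.

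**Step 2: power of the amended design.** Two-proportion z test, pooled variance under the null:

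power = Φ[(|p1 − p2| − 1.96 × SE0) / SE1]

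With n = 116 per arm, p1 = 0.20, p2 = 0.09:
- pooled rate = 0.145; SE0 = √(0.145 × 0.855 × 2/116) = 0.0462
- SE1 = √(0.20 × 0.80/116 + 0.09 × 0.91/116) = 0.0457
- (0.11 − 1.96 × 0.0462) / 0.0457 = 0.42, so power = 66.4%

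**Step 3: vary what the plan leaves open, keeping 20% vs 9%.**

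| Variant | Power |
|---|---|
| 116 vs 116, pooled z | 66.4% |
| 116 vs 116, exact power of the chi-square test | 67.3% |
| 116 vs 116, Fisher | 60.7% |
| 116 vs 116, one-sided 5% | 77.1% |
| 104 control vs 128 health-IT | 66.9% |
| 77 control vs 155 health-IT (all 232 split about 1:2) | 64.6% |
| 104 vs 104 (116 × 0.9 = 104.4) | 61.7% |

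None reaches 80%. At 1:1, 80% needs 160 per arm (320 evaluable).

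**Step 4: difference detectable at 80%.** Solving the same formula for p2 with p1 = 0.20 gives 7.4% at 116 per arm and 6.8% at 104. The relative reduction needed at 116 per arm is (20 − 7.4) / 20 = 63%, against the planned (20 − 9) / 20 = 55%.

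**Step 5: other readings of the rates, at 116 per arm.**
- Both figures as shares of the 33% readmitted: 0.33 × 0.20 = 6.6% and 0.33 × 0.09 = 3.0%. Power is about 25%.
- 33% vs 9%: above 99%. This also yields 45 per group, but it sets all readmissions against avoidable ones.
- 20% vs the preliminary 5%: 93.8%.

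**The case against.** A reader might infer that the protocol claims 80% power for the 232-patient trial. It does not. The 80% is attached to 405 evaluable patients in three groups, and the body of the document was left in its pre-amendment form throughout: it still gives 450 patients, and still excludes haemodialysis although Amendment 1 allows it. The fault is a missing figure, not a false one.

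A reader might also put the whole fall from 80% to 66% down to the smaller sample. That mixes two tests. The 80% comes from a three-group comparison; a single pair at 135 per group had about 73%. Control against the combined health-IT groups at 135 vs 270 would have had 85.8%.

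Third, the 66% depends on how the 20% is read. Taken literally, the sentence makes it a share of the 33% readmitted, and Step 5 shows how far the answer then moves. The 5% from preliminary data would leave power ample, but the plan sets that rate aside and sizes the trial on 9%.

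Fourth, a reader might infer that the dropout allowance was abandoned. Amendment 2 does not say whether 232 is enrolled or evaluable, so this cannot be established. Finally, the amendment is open about its practical reasons, and nothing in the plan says that a null result will be read as no benefit. A rule for reading such a result would be a reviewer's preference.

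All of this limits the point. What remains is that no power or detectable difference is given for the design in force, and that on the rates behind the original size no variant reaches 80%.

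**Conclusion.** The point holds as an omission that should be fixed. The plan's only power statement was not updated when Amendment 2 changed both the number of groups and the size. On 20% vs 9% of patients, two-sided 5% and an inferred 116 per arm, the amended trial has about 66% power, with a range of about 65% to 67% for unequal splits and about 62% if 10% dropout applies to the 232. It has 80% power only for 20% vs about 7.4%. That the new design has no stated power does not depend on how the rates are read; the size of the shortfall does. The patient-level reading is preferred here because it reproduces 405.

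**What to change.** Leave the target at 232. In the sample-size section and in Amendment 2:
- mark the 80% as applying to the original three-group design of 405 evaluable patients;
- for the two-group design, state the assumed rates as proportions of patients, the test and its sidedness;
- state the resulting power (about 66% for 20% vs 9%, about 62% after 10% dropout) and the difference detectable at 80% (20% vs about 7.4%), or recomputed figures if the sponsor intended other rates or another test;
- say whether 232 is enrolled or evaluable, and whether it includes patients randomised 1:1:1.

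The cost is wording only, with no extra patients or data. The stated power becomes less favourable.
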